#### Figure 3-1 Study design

# 4 Rationale

# 4.1 Rationale for study design

This study consists of a 16-week double-blind treatment period during which the efficacy and safety of secukinumab 300 mg s.c. for the treatment of patients with moderate to severe TED will be evaluated in a placebo-controlled manner, and a 52-week follow-up period. In addition, it offers a course of open-label secukinumab for participants who fail to respond to treatment at Week 16 (second course for those who received secukinumab initially and first course for those who received placebo initially), and a course of secukinumab for patients who respond at Week 16 but subsequently relapse. Following the course of open-label secukinumab there is a subsequent 24-week follow-up period.

The **randomized design** (including stratification for smoking, a key modifier of TED disease severity and response to immunosuppressive treatment of TED [Eckstein et al 2003]) ensures a comparable and balanced patient profile across treatment arms. The **placebo-controlled**, **double-blind design** allows the assessment of the efficacy and safety of secukinumab 300 mg in comparison to placebo in an adequate setting.

In case of relapse during the follow-up period, patients will be offered the option for re-treatment with open-label secukinumab 300 mg for 16 weeks (including 5 secukinumab injections during the first 5 weeks). This enables collection of data on the efficacy and safety of re-treatment in case of relapse.

Furthermore, the trial offers proptosis non-responders at Week 16 the option of a course of open-label secukinumab 300 mg s.c. (administered as above for relapsers). This will allow exploration of whether an extended treatment period could be beneficial for patients who have not achieved a sufficient response after 16 weeks of treatment. This continued treatment option will be offered to patients from both treatment arms, active as well as placebo. Since a very low rate of response under placebo treatment can be expected, this study design enables placebo treated patients to also receive a course of active treatment within this clinical trial (in case they have not achieved response at Week 16). In addition, if placebo-treated patients achieve a response and relapse (unlikely scenario), they will be offered a course of open label secukinumab.

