The course of open-label secukinumab will be a second course of active treatment for patients initially randomized to secukinumab. It will include a loading similar to the initial treatment course (i.e., weekly dosing during the first 4 weeks, 5 doses). PK modeling was performed to simulate the maximum concentration (Cmax) for patients who have received secukinumab 300 mg during the double-blind treatment phase, considering different starting time points with Week 16 as the earliest possible time point (for proptosis non-responders) (Figure 4-1). This modeling predicts a Cmax of about 120  $\mu$ g/mL, when loading is initiated at Week 16, and a somewhat lower Cmax if the loading is initiated at a later time point (e.g., Week 20 or Week 24). In case loading starts at Week 16, the predicted Cmax at approximately Week 21 is approximately 20% higher than after loading during initial treatment. No significant impact on patient safety is anticipated as short-term loading doses of higher exposure have been performed with no significant impact on safety (see Investigator's Brochure (IB)).

Patients initially randomized to placebo who receive open-label secukinumab during follow-up will follow the predicted time-concentration profile shown in Figure 4-1 without retreatment.

(ng/mL)

50

0

0

4

8

12

at Weeks 24, 25 26, 27, 28 300 mg sc g1w at Weeks 0, 1, 2, 3, 4, 300 mg sc at

Weeks 16, 17, 18, 19, 20 300 mg sc q1w at Weeks 0, 1, 2, 3, 4, 300 mg sc q4w

from Week 8

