2.1.1 General definitions

Study treatment

Novartis will supply the investigational medication listed below:

- 2 × secukinumab 150 mg PFS, s.c.
- 2 × matching placebo 0 mg PFS, s.c.

Eligible patients will be randomized in a 1:1 ratio to one of the double-blinded treatment arms.

Treatment groups

- Randomized treatment:
 - AIN457 300 mg: All patients randomized to secukinumab.
 - Placebo: Patients randomized to placebo.
- Treatment sequence:
 - **AIN457 – AIN457:** Patients randomized to secukinumab and switched to open-label secukinumab treatment in follow-up period (“AIN457 non-responder”).
 - **Placebo – AIN457:** Patients randomized to placebo and switched to open-label secukinumab treatment in follow-up period (“placebo non-responder”).

Frequency of administration

Baseline to Week 16 (Double-blind):

- Secukinumab (300 mg): Baseline, Week 1, Week 2, Week 3, Week 4, Week 8 and Week 12
- Placebo: Baseline, Week 1, Week 2, Week 3, Week 4, Week 8 and Week 12

Week 16 to end of study (EOS) (Open-label):

- Non-responders at Week 16: Secukinumab (300 mg) at Week 16, Week 17, Week 18, Week 19, Week 20, Week 24 and Week 28;
- Responders at Week 16 who relapse thereafter: Secukinumab (300 mg) at time of relapse, then 1, 2, 3, 4, 8 and 12 weeks from time of relapse.

Stratification factor

Patients will be stratified according to current smoking status (up to 20% smokers per arm), since smoking has a well-known impact on treatment efficacy in TED.

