2.2 Analysis sets

Mis-randomized patients who never received any study drug are considered as screen failures and are not included in the analysis sets.

Efficacy analysis

- The **Full analysis set (FAS)** will consist of all patients to whom study treatment (AIN457 or placebo) has been assigned. Following the intent-to-treat principle, patients will be analyzed according to the treatment they have been assigned to.

Safety analysis

The **Safety analysis set (SAF)** will consist of all patients who received at least one dose of study treatment during the treatment period. Patients will be analyzed according to the study treatment received.

Table 2-3 Treatment groups for safety analysis

Analysis period	Treatment group label
DBTP (up to Week 16)	AIN457 Placebo
Entire study period	AIN457 ¹ Placebo ² Any AIN457 ³

1 All patients randomized to secukinumab: This includes responders who receive no treatment after Week 16 and secukinumab non-responders or relapsers who go on open-label secukinumab.

2 Patients randomized to placebo with no open-label treatment in follow-up period. Any AEs reported in placebo patients prior to switching to AIN457 are also counted in this group.

3 Any AIN457 does not refer solely to just patients randomized to AIN457. It includes all patients who received at least one dose of secukinumab in DBTP or open-label follow-up. AEs occurring in placebo patients after switching to AIN457 are counted in this group.

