2.8 Safety analyses

Summaries may be performed separately for initial (Baseline to Week 16) period and entire study period (including follow-up). Week 16 is chosen due to the fact that patients may be switched to another treatment at this time. Use of data up to and including the last visit before first switch opportunity provides an unbiased comparison between AIN and placebo; data collected beyond Week 16 are included in analyses which summarize the entire study period.

All listings and tables will be presented by treatment group. Safety summaries include only data from the on-treatment period and follow-up period with the exception of Baseline data that will also be summarized where appropriate (e.g., change from Baseline summaries). The on-treatment period is defined as date of first treatment to (date of last treatment + 84 days).

In addition, a separate summary for death including on-treatment and post-treatment deaths will be provided.

In particular, summary tables for AEs will summarize only on-treatment events, with a start date during the on-treatment period (treatment-emergent AEs) for the DBTP and the entire study period.

Missing data will not be imputed for safety endpoints.

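### The SAP defines the two open-label treatment sequences but plans no adverse-event summary of the open-label course by sequence, so an excess on re-loading would be diluted in pooled rates and shown separately only in listings

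*Protocol*

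**What the plan says.** **Exposure.** Protocol 4.2 predicts a Cmax of about 120 µg/mL "when loading is initiated at Week 16, and a somewhat lower Cmax if the loading is initiated at a later time point". For the Week 16 start it adds that "the predicted Cmax at approximately Week 21 is approximately 20% higher than after loading during initial treatment". This excess is stated for the Week 16 start only, that is, for proptosis non-responders first randomized to secukinumab. On safety the same section says: "No significant impact on patient safety is anticipated as short-term loading doses of higher exposure have been performed", and it refers to the Investigator's Brochure.

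**Purpose.** Protocol 4.1 says of relapsers: "This enables collection of data on the efficacy and safety of re-treatment in case of relapse". Of Week 16 non-responders it says: "This will allow exploration of whether an extended treatment period could be beneficial". Protocol 6.1.3 mentions safety in connection with the 24-week follow-up of non-responders, although the sentence is incomplete in the public copy. The formal safety objective is secukinumab compared with placebo.

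**Groups.** SAP 2.1.1 defines AIN457–AIN457 as "Patients randomized to secukinumab and switched to open-label secukinumab treatment in follow-up period", and Placebo–AIN457 in parallel. Table 2-3, which sets the safety columns, uses AIN457, Placebo and Any AIN457 instead. In the entire-study tables AIN457 holds everyone randomized to secukinumab, including those who take the open-label course. Of Any AIN457 the footnote says: "It includes all patients who received at least one dose of secukinumab in DBTP or open-label follow-up".

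**Periods and counting.** SAP 2.8 and Table 2-4 give two periods, Day 1 to Week 16 and the entire study. Table 2-4 lists the exposure-adjusted rate for the entire study only. SAP 5.4.3 bases that rate on time to first occurrence. The single worked example, Table 5-1, restarts time at risk when a placebo patient moves to AIN457; it has no AIN457-to-AIN457 case.

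**The concern.** The protocol makes a specific prediction about one group (a higher peak) and a specific expectation (no significant safety consequence). A reader of the clinical study report would look for the adverse events of that group in that course and would find no summary table that shows them.

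Three features combine:

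- Both active entire-study columns contain the second course mixed with first courses.
- A patient who had a given event in the first course is no longer at risk of it in the second, so recurrences on re-loading drop out of the rate.
- No first-course exposure-adjusted rate is listed to set beside the entire-study rate.

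Superiority testing has been dropped and the SAP is now purely descriptive, so the safety description is one of the main remaining outputs. SAP 2.4.2 already displays concomitant medications separately for the double-blind and follow-up periods, but adverse events are not split in this way.

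**Working it through.** **1. The plan's own figure.** The documents give no half-life or absorption rate, so the 20% cannot be reproduced exactly. I superposed equal doses in a one-compartment model with immediate absorption: doses at Weeks 0, 1, 2, 3, 4, 8 and 12, then five weekly doses from the re-start, with the half-life assumed. The ratio of second to first peak for a Week 16 start is:

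| Assumed half-life (days) | Week 16 start |
|---|---|
| 21 | 1.09 |
| 27 | 1.15 |
| 30 | 1.19 |
| 35 | 1.24 |

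Protocol 4.2 gives a trough of 38 µg/mL and implies a first peak of 120 / 1.2 = 100 µg/mL. Together these fit a half-life near 38 days and a ratio of about 1.27. So 20% is plausible. At a 30-day half-life the ratio falls to 1.10 for a Week 20 start, 1.05 for Week 24 and 1.00 for Week 52, in line with the protocol's statement about later starts.

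**2. Windows.** The double-blind period runs from Day 1 to Day 113, which is 112 days. The open-label course runs from Day 113 to the last dose at Day 197 plus 84 days, which is Day 281, or 168 days if completed.

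**3. Dilution in the pooled rate.** Assume a constant first-event rate λ in course 1 and 2λ in course 2. Let S1 = exp(−112λ) and S2 = exp(−336λ), with λ per day. The SAP rate is D/T, where, per patient,

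- D = 1 − S1·S2
- T = (1 − S1)/λ + S1(1 − S2)/(2λ)

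At 1 event per patient-year, S1 = 0.736 and S2 = 0.399, so D = 0.707 and T = 0.485 patient-years. The rate is 0.707 / 0.485 = 1.46, against 1 in course 1. For Any AIN457 I assume equal numbers of placebo switchers, each with one 168-day course at rate λ.

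| Assumed course-1 rate (per patient-year) | Already counted before re-loading | Pooled AIN457 / course 1 | Any AIN457 / course 1 |
|---|---|---|---|
| 0.2 | 6% | 1.57 | 1.35 |
| 1 | 26% | 1.46 | 1.26 |
| 4 | 71% | 1.17 | 1.08 |

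For very rare events the AIN457 ratio tends to (112 + 2 × 168) / 280 = 1.60, which is the most a true doubling can show. Single preferred terms usually sit near the top rows, and the any-adverse-event row near the bottom.

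**4. Crude incidence.** At 1 event per patient-year the AIN457 column goes from 26% at Week 16 to 71% over the entire study with a doubled rate, and to 54% with no excess. The 54% is not printed anywhere, so the reader cannot tell longer exposure from a higher rate.

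**5. Why a crude open-label column alone would mislead.** With no re-loading effect at all, an incidence of 70% in 112 days becomes 1 − 0.30^(168/112) = 84% in 168 days, and 50% becomes 65%. Unequal windows would produce a false excess, so rates are needed for both periods.

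**6. What the split can deliver.** SAP section 1 reports 28 randomized, 25 completing the double-blind period and 23 entering follow-up over both arms. The number re-treated after secukinumab is not given; I assume 8 to 14. The approximate two-sided 5% power to distinguish 30% from 60% with equal groups is 21% at 8 per group, 31% at 12 and 35% at 14.

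**The case against.** The strongest reply is that the information is not lost. SAP 2.8.1 lists all adverse events, and with so few patients the listings can be read. Clinically notable laboratory values are summarised by treatment and visit (SAP 2.8.3), with separate visit windows for re-treated non-responders in Table 2-2; this covers neutrophils, which Protocol 4.5 singles out for these patients. Some recovery by subtraction is also possible. Any AIN457 minus AIN457 roughly gives the placebo switchers. Entire-study AIN457 minus double-blind AIN457 gives patients whose first event came after Week 16. This stands, and it rules out the inference that an excess on re-loading could not be seen at all. Subtraction does not recover recurrences, however, nor a rate for the second course.

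It is also tempting to say that the plan fails a stated purpose. The explicit sentence on the safety of re-treatment concerns relapsers, whereas the 20% concerns Week 16 non-responders. SAP 1.2 reports no responders at termination, so the relapser sentence is largely moot. For non-responders, Protocol 4.1 names possible benefit; only the incomplete sentence in 6.1.3 points to safety.

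Finally, a doubled rate is a strong assumption for a 20% higher peak, given that Protocol 4.5 reports no dose dependency of overall adverse-event rates between 300 mg and 150 mg. That is fair: the doubling is used here only to measure dilution.

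**Conclusion.** The point holds as a gap in presentation. No planned summary table isolates the adverse events of the open-label course by sequence, although the sequences are defined and the protocol makes a particular safety statement about one of them. Under a true doubling, the entire-study AIN457 rate would show a ratio between about 1.2 and 1.6, depending on how common the event is, and could not be attributed to a course.

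These sizes rest on assumed event rates, constant hazards, a completed second course and, for Any AIN457, equal group sizes. None of these is given in the documents.

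A reader might infer that re-loading is unsafe, or that this course supplies most of the secukinumab safety data after Week 16. The documents support neither. They contain no adverse-event data; placebo switchers also contribute after Week 16; the split of the 23 patients is not reported; and open-label treatment was optional. Nor would a separate table confirm or refute the protocol's expectation with these numbers. It would make the course visible, which is what a descriptive SAP can offer.

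**What to change.** In SAP Tables 2-3 and 2-4, add a third analysis period for the open-label course, from the first open-label dose to the earlier of last dose + 84 days and end of study. Use the columns already defined in SAP 2.1.1, AIN457–AIN457 and Placebo–AIN457.

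- Restart event counting and time at risk at the first open-label dose in both columns, and add an AIN457-to-AIN457 row to Table 5-1 that shows this.
- Give exposure-adjusted rates for the open-label course and for the double-blind period. State that crude percentages from the two periods are not comparable, because the windows are up to about 168 and 112 days.
- Name Placebo–AIN457 as the same-window comparator for AIN457–AIN457.
- Produce the overview, SAE and SOC/PT tables for this period and label them descriptive.

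The change needs SAP wording and one more set of tables from data already collected, with no change to conduct. The downside is small columns with little power, to be read descriptively beside the listings.

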# Figure 4-1 PK modeling of second treatment course including initial loading 150 300 mg sc at Weeks 0, 1, predicted secukinumab concn. 2, 3, 4, 8, 12, 300 mg sc at Weeks 20, 21 22, 23, 24 300 mg sc at Weeks 0, 1, 100 2, 3, 4, 8, 12, 300 mg sc

16 20 24 28 32 36

#### 4.3 Rationale for choice of control drug (placebo)

Time (week)

Placebo has been selected for the control arm, as it enables the best measure of efficacy of secukinumab in the treatment of moderate to severe TED. Furthermore, placebo will be given for a limited duration of 16 weeks.

Except for teprotumumab (approved by FDA in Jan 2020), which is only available in the United States, there is no approved therapy for patients with active, moderate to severe TED as described in Section 1. Systemic corticosteroids are used in some patients, but they are characterized by sub-optimal efficacy with very limited impact on proptosis, a high relapse rate, marginal impact on long-term outcomes, as well as toxicity concerns.

Other immunomodulatory compounds tested in TED, e.g., teprotumumab, rituximab or tocilizumab, were also tested in comparison to placebo for up to 24 weeks (Stan et al 2015, Perez-Moreiras et al 2018, Douglas et al 2020).

Risks will be minimized by very frequent, careful ophthalmologic monitoring of signs of disease progression. In case of worsening of TED the patient should be discontinued from study drug at the discretion of the investigator (also refer to Section 9.1.1). Furthermore, the risk is minimized by the in- and exclusion criteria of the trial, which ensure that high-risk patients with high disease activity, need for surgery or signs of optic neuropathy are excluded from this study.

#### 4.4 Purpose and timing of primary analysis

The primary analysis will be performed after all patients have completed Week 40 assessments and it will include the primary endpoint (Week 16) and relapse rate data up to 24 weeks following the end of treatment. This will support potential regulatory filing. A final analysis is planned at the EOS once all patients have completed their EOS visit. There may be other analyses between Week 40 and Week 108 to support other regulatory filings.

## 4.5 Risks and benefits

Secukinumab has demonstrated a positive benefit-risk ratio in the treatment of several chronic inflammatory conditions for which IL17A plays a central role, including plaque-PsO, PsA, AS and nr-axSpA. As IL-17A has been recognized as an important mediator in the immuno-pathogenesis of TED, secukinumab will potentially have beneficial effects for patients with TED by inhibiting IL-17A-driven inflammation which may reduce disease activity, tissue expansion, and fibrosis. As placebo patients who are non-responders at Week 16 have the option to receive secukinumab, they will also have this potential benefit.

The safety data from the completed and ongoing studies across various indications including AE and SAE data, laboratory parameters and immunogenicity data demonstrate a consistent and favorable safety profile. No dose dependency with secukinumab (300 mg vs. 150 mg) has been observed with respect to overall rates of AEs/SAEs in the clinical development program. Details of the risks and benefits are outlined in the current version of the IB.

Furthermore, extensive post-approval real-world evidence has been generated in clinical practice, confirming the favorable safety profile observed in the development program.

Observed risks include infections, in particular, upper respiratory tract infections, neutropenia and hypersensitivity reactions that can be seen with administration of foreign proteins. Most of the infections were non-serious, mild to moderate in severity, clinically easily manageable and did not lead to treatment discontinuation. Cases of neutropenia were uncommon, generally mild to moderate, and transient and did not lead to treatment discontinuation.

Patients randomized to the placebo arm will not receive active treatment with secukinumab during the first 16 weeks of the trial. However, they will be monitored very closely in order to identify any progression or need for other treatment. If they have not achieved a proptosis response at Week 16, they have the opportunity to receive a course of active secukinumab treatment starting at Week 16.

In case of worsening of the disease and need for other treatment or therapeutic interventions, e.g., orbital decompression, investigators and patients can stop study treatment at any time and apply other treatments as needed.

The risk to patients in this trial will be further minimized by compliance with the eligibility criteria, close clinical monitoring and extensive guidance to the investigators, provided in the current version of the IB.

Women of childbearing potential must be informed that taking the study treatment may involve unknown risks to the fetus if pregnancy were to occur during the study, and agree that in order to participate in the study they must strictly adhere to the contraception requirements outlined in the exclusion criteria. If there is any question that the patient will not reliably comply, they should not be entered or continue in the study.

Taking into account the individual risks, the expected risk profile of secukinumab from a mechanism of action perspective in patients with TED is anticipated to be similar to that of the approved indications. Novartis is not aware of any scientific evidence that would indicate potential differences in the safety profile of secukinumab between patients with TED and patients with PsO, PsA, AS or nr-axSpA. Patients with TED are usually on treatment with

Novartis	Confidential	Page 40 of 99
Amended Protocol (Version No. 0	2 Track Changes)	Protocol No. CAIN457ADE16

anti-thyroid medication and therefore at a potentially higher risk for developing neutropenia, which will be carefully monitored by regular blood tests throughout the study.

The bothersome symptoms of active, moderate to severe TED, the significant impact on patient's quality of life, the potential long-term functional impairment and the very limited availability of effective and safe treatment options for these patients lead to a very high degree of unmet medical need in the treatment of this indication. The well-established, consistent and favorable safety profile of secukinumab and the potential of secukinumab to reduce disease activity, improve symptom severity and improve long-term functional outcome in patients with TED, suggest that participation in this trial offers a well justifiable benefit-risk profile.

